### 9.2.2. Assigning Attribution of Adverse Events

The PI must attempt to determine the cause of each event. Every effort will be made by the PI to assess the relationship of each AE to study drug. To ensure consistency of AE/SAE causality assessments, PI(s) should apply the following guideline:

**Related:** There is an association between the event and the administration of study drug, a plausible mechanism for the event to be related to the study drug and causes other than the study drug have been ruled out, and/or the event re-appeared on re-exposure to the study drug.

**Possibly Related:** There is an association between the event and the administration of the study drug and there is a plausible mechanism for the event to be related to study drug, but there may also be alternative etiology, such as characteristics of the subject’s clinical status or underlying disease.

**Unlikely Related:** The event is unlikely to be related to the study drug and likely to be related to factors other than study drug.

**Not Related:** The event is related to an etiology other than the study drug (the alternative etiology must be documented in the study subject’s medical record).

### 9.2.3. Classifying Action Taken with Study Drug

In the case of an AE, the actions that can be taken with study drug are defined below in [Table 4](#).

**Table 4: Options for Action Taken with Study Drug**

Classification	Definition
Dose Not Changed	Study drug dose not changed in response to the AE
Dose Reduced	Not Applicable
Drug Interrupted	Study drug administration interrupted in response to an AE
Drug Withdrawn	Study drug administration permanently discontinued in response to an AE
Not Applicable	Action taken regarding study drug administration does not apply. “Not applicable” should be used in circumstances when no opportunity to decide whether to continue, interrupt or withdraw treatment was possible such as when the investigational treatment had been completed before the adverse event began.

#### 9.2.4. Classifying Adverse Event Outcome

[figure not shown]
For every AE/SAE, the possible outcomes of the event and the definition of the outcome are shown below in Table 5. One outcome must be entered into the appropriate field on the AE and (if appropriate) SAE form for each event as discussed in the eCRF instructions.

**Table 5: Classification and Definition of AE Outcomes**

Classification	Definition
Recovered / Resolved	Resolution of an AE with no residual signs or symptoms
Recovered / Resolved with sequelae	Resolution of an AE with residual signs or symptoms
Is Recovering / Is Resolving	Incomplete improvement to date but AE continues to improve/resolve and complete resolution is expected over time
Not Recovered / Not Resolved	Either incomplete improvement or no improvement of an AE, such that it remains ongoing
Fatal	Outcome of an AE is death. "Fatal" should be used when death is at least possibly related to the adverse event.
Unknown	Outcome of an AE is not known (e.g., a subject lost to follow up)

#### 9.2.5. Documenting and Reporting Serious Pretreatment Events and Serious Adverse Events

All SAEs that occur after obtaining informed consent through the EOS/Follow-up visit, regardless of causality, must be reported by the PI to [REDACTED] and Enanta within 24 hours of learning of its occurrence. In addition, all SAEs that occur after the EOS Visit and that are considered possibly related to study drug(s) and all deaths must also be reported within 24 hours of learning of its occurrence. Additional details are provided in the Safety Management Plan. All SAE reporting will be done primarily via email; fax will be the back-up means of communication. All new/initial events as well as follow-up information on previously reported events should be communicated via e-mail. PIs are asked to report follow up information as soon as it becomes available, to ensure timely reporting to Health Authorities.

SAEs will be recorded on the SAE Form using a recognized medical term or diagnosis that accurately reflects the event. SAEs will be assessed by the PI for severity, relationship to the investigational study drug(s) and possible etiologies. Relationship to study drug(s) will be recorded on the SAE form. For the purposes of study analysis, if the event has not resolved at the end of the study reporting period, it will be documented as ongoing. For purposes of regulatory safety monitoring, the PI is required to follow the event to resolution and report the outcome of the event to the PRA Safety and Risk Management using the SAE Form.

The PI is responsible for notifying [REDACTED]/the Sponsor within 24 hours of identifying an SAE, regardless of the presumed relationship to the investigational study drug. The SAE Form should be completed for new/initial events as well as to report follow-up information on previously reported events. The PI is asked to report follow-up information as it becomes available.

Enanta or its designees, as study Sponsor, is responsible for reporting suspected, unexpected, serious adverse reactions (SUSARs) involving the study drug(s) to all regulatory authorities, and participating PIs, in accordance with FDA, International Conference on Harmonization (ICH) Guidelines, and/or local regional or country regulatory requirements, as applicable.

#### **9.2.6. Documenting and Reporting of Pregnancy**

Females must not become pregnant while taking study drug. However, as a precaution, all subjects will be counseled to inform the PI of any pregnancy that occurs during study treatment and for 90 days after the last dose of study drug.

If a female subject or the female partner of a male subject becomes pregnant while participating in the study, study treatment must be permanently discontinued immediately. The PI must notify the Sponsor's Medical Monitor and [REDACTED] within one business day of the sites' knowledge of the subject's (or partner's) pregnancy, by utilizing the study-specified pregnancy report form. If confirmed to be on active drug, the subject or partner will be followed until end of pregnancy and the infant will be followed for one year after the birth, provided informed consent is obtained. A separate ICF will be provided to explain these follow-up activities. Pregnancy itself does not constitute an AE.

#### **9.3. Follow-up of Adverse Events and Serious Adverse Events**

Follow all AEs (serious and nonserious) until resolution or otherwise explained (see [Table 5](#)), the subject dies, the event stabilizes and is not expected to further resolve with the maximum time limit for stabilization defined as 30 days after the occurrence of the event, or when alternative therapy is instituted, whichever occurs first. If alternative therapy is instituted, it should be documented. Enanta may request that the PI perform or arrange for supplemental measurements or evaluations to further clarify the nature of the event.

#### **9.4. Sponsor's Review of Adverse Events and Serious Adverse Events**

Enanta will maintain an ongoing review of all AEs and SAEs.

#### **9.5. Data Safety Monitoring Board**

Safety data from this study will be reviewed by a Data Safety Monitoring Board (DSMB) throughout the study. The DSMB will be headed by a DSMB Chair and will include physicians with expertise in diseases of the liver including NASH. Procedures for data review including timing and potential outcomes will be governed by the DSMB charter.

## 10. SUBJECT SAFETY MANAGEMENT

### 10.1. Individual Subject Stopping Rules

Study drug will be discontinued in subjects with elevated ALT or AST (see below) and thorough evaluation and follow-up will be performed. Study drug will be discontinued once any one of the thresholds presented below is met. No repeat test is required. Reference Baseline is defined as the mean of Screening and Day 1 values. The following study drug stopping rules are applied:

- If ALT or AST increases to  $>5\times$  Reference Baseline (and is at least  $> 5x$  ULN)
- If ALT or AST increases to  $>2\times$  Reference Baseline (and is at least  $> 3x$  ULN) AND the increase is accompanied by
  - a concomitant total bilirubin increase to  $>2\times$  Reference Baseline (and at least  $> 2x$  ULN) **OR**
  - the INR is concomitantly  $> 1.5$
- If ALT or AST increases to  $>2\times$  Reference Baseline (and is at least  $> 3x$  ULN) **AND**
  - elevations of ALT/AST are accompanied by signs or symptoms of right upper quadrant abdominal pain, anorexia, nausea, vomiting, fever, eosinophilia ( $>$  upper limit of normal of absolute eosinophilia count), and/or rash.

Refer to Section 10.2 for close monitoring guidelines for subjects who meet criteria for drug discontinuation due to elevated ALT/AST.

### 10.2. Management of Liver Enzyme Elevations

The FDA Guidance for Industry for Drug-Induced Liver Injury (*FDA, 2009*) provides guidance for the management of changes in liver transaminases (ALT/AST).

Close monitoring activities will be initiated:

- If ALT or AST increases  $> 2x$  Reference Baseline (and is at least  $> 3x$  ULN) **OR**
- If ALT or AST increases  $> 8x$  ULN (whichever comes first)

Following the initial alert, sites will be asked to perform the following laboratory tests and assessments within 48 – 72 hours.

- Blood samples must be taken prior to taking study drug on that day (i.e., predose).
  - Clinical Chemistry: ALT, AST, GGT, total bilirubin, direct bilirubin, indirect bilirubin, ALP
  - Hematology: full red blood count
  - Coagulation: INR
  - PK sample: predose
- Physical examination for detection of accompanying clinical symptoms potentially associated with deviation in liver function e.g. right upper quadrant abdominal pain, anorexia, nausea, vomiting, fever, or rash.
- Sites will also be requested to comment/confirm
  - if the subject has any history of regular alcohol consumption exceeding 14 drinks/week for females and 21 drinks/week for males within 6 months of Screening as well as any recent relevant alcohol intake

- if the subject started any new medications recently including non-prescription medications and herbal and dietary supplement preparations, recreational drug use, special diets, or was recently exposed to environmental chemical agents

Should retest results not meet close monitoring cut-offs, a second retest will be requested within 48 – 72 hours. If the second retest is negative, the event will be closed and attributed to the fluctuating nature of liver transaminases.

The following close observation guidelines apply to subjects for whom the repeat assessment shows persistent elevations of transaminases but who do not meet drug discontinuation criteria, and for subjects who discontinue study drug due to ALT/AST elevations (no repeat test required to confirm IMP stopping rule). The following laboratory tests and assessments will be performed at every visit until retest results no longer meet close monitoring criteria.

- Blood samples must be taken prior to taking study drug on that day (i.e., predose).
  - Clinical Chemistry: ALT, AST, GGT, total bilirubin, direct bilirubin, indirect bilirubin, ALP
  - Hematology: full red blood count
  - Coagulation: INR
  - PK sample: predose
- Physical examination for detection of accompanying clinical symptoms potentially associated with deviation in liver function e.g. right upper quadrant abdominal pain, anorexia, nausea, vomiting, fever, or rash.
- **At the first visit following confirmation of close monitoring criteria/the next visit after meeting IMP stopping rules**, a blood sample will be taken for viral hepatitis A, B, C, D, E as well as Cytomegalovirus (CMV) and Epstein Barr Virus (EBV).

The table below (Table 6) shows the recommended retest frequency based on the course of liver transaminase retest results. The recommendations were adapted from the FDA guidance on Drug-Induced Liver Injury (FDA, 2009).

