### 7.1.3. Treatment Period Visits (Day 7 through Week 72/EOT)

**Phone Contact:** On Day 7, sites will contact subjects by phone to assess AEs, inquire about concomitant medications taken during the past week, and confirm subjects are taking study drug appropriately. Site personnel will also remind subjects to complete the pruritus visual analog and 5D-itch scales and to bring the scales back with them to the next clinic visit.

At Weeks 52, 60 and 68, the site will contact the subject by phone to assess drug accountability, concomitant medications, and AE/SAEs. In addition, for females of child-bearing potential, the site will confirm that the at-home pregnancy test was performed and that the results were negative. If the results were positive, the procedures listed in Section 8.4.6 should be followed.

**Clinic Visits:** All subjects will be requested to return to the clinic for on-treatment study visits as follows: Weeks 2, 4, 8, 12, 16, 20, 24, 28, 32, 36, 40, 44, 48, 56, 64, and 72 following the Day 1 (initial dosing) visit. Note that all treatment visit weeks are determined based on day of initial

dosing. Subjects will be instructed to fast overnight for a minimum of 8 hours prior to each visit so that safety laboratory samples can be drawn fasted. Treatment period assessments per visit are shown in the [Schedule of Assessments](#).

Refer to Section 5.7 for instructions on study drug dosing. Refer to Section 8.4 for instructions on collection of safety laboratory samples.

At the end of the treatment period, subjects will complete the EOT visit. Subjects who complete the full scheduled 72 weeks of treatment will complete the EOT assessments at the Week 72 visit. Subjects who discontinue treatment early should complete EOT assessments at the time of treatment discontinuation (if in the clinic) or within one week following last dose of study drug if the subject discontinues treatment while not in the clinic. Procedures performed are specified in the [Schedule of Assessments](#).

Subjects should take their last dose of study drug in the clinic at the Week 72 visit.

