### **8.4. Clinical Laboratory and Diagnostic Procedures**

All laboratory samples will be analyzed by a centralized laboratory (i.e., ICON Laboratory) or designee. A laboratory reference manual will be provided to the site detailing kit contents, reordering supplies, sample collection (see below), handling, storage and shipment instructions. All unblinded laboratory values will be reviewed by the PI, documented, and the results maintained in the source documents. All out-of-range lab findings require an interpretation as to whether or not they are of clinical significance. Clinically significant laboratory findings in the opinion of the PI must be recorded as an AE (or SAE as appropriate) (Section 9.1).

Blood samples for safety assessments should be collected predose for visits where study drug is administered in the clinic or at least 4 hours postdose if the subject took study drug at home (see Section 5.7 regarding when study drug is taken at home by the subject versus in the clinic during the visit). Additional samples collected for PK and PD analysis should be collected postdose as noted in the [Schedule of Assessments](#). Additional clinical laboratory evaluations will be performed at other times if judged clinically appropriate by the PI, or if the safety review of the data suggests a more detailed assessment of clinical laboratory safety evaluations.

For selected biomarker analysis, serum or plasma samples should be collected for analysis of FGF-19, BAs, and C4 as indicated in the [Schedule of Assessments](#) and according to instructions provided in the laboratory reference manual.

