**Table 3: Laboratory Evaluations**

CHEMISTRY PANEL Alanine Aminotransferase (ALT/SGPT) Albumin, Serum Albumin/Globulin (A/G) Ratio (calculation) Alkaline Phosphatase, Serum Amylase Aspartate Aminotransferase (AST/SGOT) Bilirubin, Total, Indirect and Direct Blood urea nitrogen (BUN) BUN/Creatinine Ratio (calculation) Calcium, (Serum) Creatine Kinase Creatinine, Serum (and eGFR [MDRD]) Uric Acid Electrolyte Panel (Na+, K+, Cl, Bicarb.) Phosphorus Gamma Glutamyl Transferase (GGT) Globulin, Total Lactate Dehydrogenase (LDH) Lipase Protein, Total, Serum HbA1c HOMA indices Fasting Insulinemia Fasting Plasma Glucose Total Cholesterol (TC) Triglycerides (TG)
	
HEMATOLOGY PANEL Hemoglobin Hematocrit Differential WBC Count (percentage and absolute): Basophils, Eosinophils, Lymphocytes, Monocytes, Neutrophils Mean corpuscular hemoglobin (MCH) Mean corpuscular hemoglobin concentration (MCHC) Mean corpuscular volume (MCV) Platelets Red Blood Count (RBC) White Blood Cell (Count) (WBC)
 
VIRAL DETECTION FOR ENTRY CRITERIA Human immunodeficiency virus (HIV)-1, HIV-2, Hepatitis B virus (HBV) (Hepatitis B surface antigen [HBsAg]), hepatitis C virus (HCV)
 
MARKERS OF CV RISKS AND LIPIDS Triglycerides (TG) apoB Total Cholesterol (TC) High Density Lipoprotein – Cholesterol (HDL-C) Low-Density-Lipoprotein – Cholesterol (LDL-C) Total/HDL Cholesterol (CT) Ratio Adiponectin

URINALYSIS Routine urinalysis to include: Color and appearance, pH, SG, Bilirubin, Glucose, Ketones, Leukocytes, Nitrite, Occult blood, Protein, Urobilinogen, Microscopic (including RBCs and WBCs)
	
BIOMARKERS FOR NASH Cytokeratin (CK)18 GLP-1 (glucagon-like peptide-1)
 
PD MARKERS FOR FXR ACTIVITY: Fibroblast growth factor (FGF)19 Total bile acids (BAs) C4 (7<math>\alpha</math>-OH-4-cholesten-3-one)

PREGNANCY AND OTHER TESTS Serum pregnancy test Follicle-StimulatingHormone (FSH)
	
FIBROSIS AND INFLAMMATORY MARKERS ENHANCED LIVER FIBROSIS (ELF) PANEL -Hyaluronic acid (HA), -Procollagen III amino terminal peptide (PIIINP) -Tissue inhibitor of metalloproteinase 1 (TIMP-1)

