**Table 6: Retest Frequency Recommendations**

Trends Observed for Repeat Liver Function Test	Frequency for Repeat Tests
First 3 repeat tests (including test to confirm initial alert test result)	Every 48 – 72 hrs
Increasing tendency of test result	Every 48 – 72 hrs
Stabilization of test result	Once weekly
Decreasing tendency	Once weekly – every 2 weeks

Depending on the course of the liver transaminase retest results, on a case-by-case basis, a gastroenterology or hepatology consultation or additional liver biopsy for any subject with persistent evidence of liver injury might be indicated.

If a subject lives in a remote area, they can be tested locally with the results promptly communicated to the PI site. However, testing via central lab is the preferred option.

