-  Height to be assessed at Screening only.
-  Full physical exam (PE) at Screening, Week 12, and EOS Visit; subsequent PE should be targeted to review new signs and symptoms.
-  Vital Signs include heart rate, respiratory rate, blood pressure, and will be measured predose.
-  Safety laboratory tests include chemistry (including liver function tests), hematology, and urinalysis and should be collected predose at all visits; See Table 3 for details. eGFR will be calculated at all visits based on the MDRD formula. HbA1c will be obtained at Screening, Baseline, week 12, and Week 72..
-  Pruritus scales (up to 2 scales) will be utilized to measure pruritus for every subject regardless of whether or not a subject experiences pruritus. Please refer to Section 8.3.5 and additional details included in the study binder.
-  QoL includes SF-36 and CLDQ-NASH. In addition, Dermatology Life Quality Index (DLQI) will be completed at each in-clinic visit by subjects who reported pruritus until resolution. Additional details can be found in the study binder.
-  Lipids and CV risk markers to be collected are detailed in Table 3.
-  Markers of inflammation include fibrinogen, CRP, IL-6, IL-1 $\beta$ , TNF- $\alpha$ , TNF- $\beta$ , alpha2 macroglobulin and haptoglobin (See Table 3).
-  One sample will be collected from all subjects predose.
-  Samples should be collected before the subject takes the daily dose of study drug. On Day 1 and Weeks 12, 36, and 72, samples should be collected predose and two samples postdose; the first postdose sample will be collected 1 to 3 hours after dosing and the second collected at least 1 hour later. At all other visits, samples will be collected only predose. If the subject took drug prior to their clinic visit, only one postdose sample should be collected.

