-  PK predose samples should be collected before the daily dose of study drug. On Day 1 and Weeks 12, 36, and 72, one PK sample should be collected predose and two samples postdose; the first postdose sample should be collected 1 to 3 hours postdose and the second postdose sample at least 1 hour later. At all other visits, PK samples will be collected predose. If the subject took drug prior to their clinic visit, only one postdose sample should be collected. For subjects who discontinue treatment early, collect one postdose sample at the EOT visit. For subjects with persistent transaminase or ALP elevations and evidence of liver injury and who remain on study drug, the one additional PK sample will be collected at each visit where safety labs are obtained.
-  See Section 5.7 for details.

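### The liver retest lists ask only for a red cell count, so the eosinophil count that one stopping rule needs is not required between scheduled visits

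*Protocol*

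**What the plan says.** Protocol Section 10.1 lists the individual stopping rules. Any one of them is enough, and no repeat test is needed. The third applies when ALT or AST is above twice Reference Baseline and above 3x ULN, together with at least one of seven signs or symptoms. Six are clinical: right upper quadrant pain, anorexia, nausea, vomiting, fever and rash. The seventh, eosinophilia, is a laboratory value, defined as exceeding the "upper limit of normal of absolute eosinophilia count".

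Section 10.2 starts close monitoring at the same transaminase level, or at ALT or AST above 8x ULN. It gives one list of tests for 48–72 hours after the alert and another for every visit under close observation. In both, the hematology item reads "Hematology: full red blood count".

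The scheduled safety panel is wider. The hematology panel in Table 3 has a line "Differential WBC Count (percentage and absolute): Basophils, Eosinophils, Lymphocytes, Monocytes, Neutrophils", with red blood count as a separate line. Footnote 14 of the Schedule of Assessments says: "Safety laboratory tests include chemistry (including liver function tests), hematology, and urinalysis and should be collected predose at all visits".

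Some closely monitored subjects are expected to continue dosing. Section 10.2 covers persistent elevations that do not meet a discontinuation criterion, and footnote 21 of the Schedule adds a PK sample "For subjects with persistent transaminase or ALP elevations and evidence of liver injury and who remain on study drug".

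**The concern.** A subject who enters close monitoring through the 2x Reference Baseline / 3x ULN threshold already meets the transaminase half of the third stopping rule. Eosinophilia alone would complete it. That subject stays on drug only because no stopping rule is known to be met, and the repeat draws exist partly to detect when that changes.

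Taken as written, those draws cannot detect new eosinophilia. It also cannot be found by physical examination, so the blood list was its only required route. If it develops after the alert draw, with no listed symptom and no bilirubin, INR or 5x trigger, dosing could continue until the next scheduled panel although the protocol requires it to stop. SAP Section 8.7.2 tabulates subjects who meet these rules, so an unmeasured event would also be missing from that table.

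**Working it through.** **Step 1. Match each stopping-rule component (Section 10.1) to the required repeat assessments (Section 10.2).**

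| Component in 10.1 | Required in both 10.2 lists? |
|---|---|
| ALT, AST | Yes, chemistry |
| Total bilirubin | Yes, chemistry |
| INR | Yes, coagulation |
| Right upper quadrant pain, anorexia, nausea, vomiting, fever, rash | Yes, physical examination |
| Absolute eosinophil count | No: red cell count only, and not among the examination items |

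Three of the four laboratory criteria (ALT/AST, bilirubin, INR, eosinophils) are covered. Eosinophils are not.

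**Step 2. Gaps between required eosinophil counts.** Section 7.1.3 puts on-treatment clinic visits at "Weeks 2, 4, 8, 12, 16, 20, 24, 28, 32, 36, 40, 44, 48, 56, 64, and 72"; Weeks 52, 60 and 68 are phone contacts. Nominal gaps, ignoring visit windows:

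- Day 1 to Week 2 and Week 2 to Week 4: 2 × 7 = 14 days
- Week 4 to Week 48: 4 × 7 = 28 days
- Week 48 to Week 72: 8 × 7 = 56 days

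**Step 3. Off-schedule draws within each gap.** Take an alert at a scheduled visit as day 0. Under Table 6 the first three repeats are every 48–72 hours, so the third falls on day 6 (2-day step) or day 9 (3-day step). After that, draws continue every 2–3 days if values are rising, every 7 days if stable, and every 7 to 14 days if falling; the 14-day interval is used below. Only draws strictly before the next scheduled panel are counted.

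Example, stable values in a 28-day gap: days 2, 4, 6, 13, 20, 27 gives 6 draws; days 3, 6, 9, 16, 23 gives 5.

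| Gap | Rising (2-day / 3-day step) | Stable | Falling, 2-weekly |
|---|---|---|---|
| 14 days | 6 / 4 | 4 / 3 | 3 / 3 |
| 28 days | 13 / 9 | 6 / 5 | 4 / 4 |
| 56 days | 27 / 18 | 10 / 9 | 6 / 6 |

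None of these draws has a required eosinophil count. In practice the 14-day row concerns Week 2 to Week 4. Reference Baseline is the mean of the Screening and Day 1 values, so a Day 1 value cannot exceed twice it.

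**Step 4. Number of subjects.** The documents give no rate of entry to close observation. Assuming 1–5% of the planned 336: 0.01 × 336 = 3.4 and 0.05 × 336 = 16.8, or about 3–17 subjects. Those with isolated new eosinophilia while on drug between panels would be a fraction of these, possibly none.

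**The case against.** There are five points on the other side.

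- **Cross-reference in Section 8.4.5.1.** It asks for an extra PK sample, at visits with safety labs, from subjects with persistent elevations, and points to Section 10.2. One could infer that repeat visits carry the full safety panel, differential included. But Section 10.2 sets its own shorter list for these draws, and footnote 14 annotates the table of planned visits. The specific list governs.
- **A wording slip.** The phrase may have been meant as full blood count. That is plausible, but the text is then wrong in two places, and a full blood count does not clearly require a differential.
- **Kit contents.** The laboratory manual, which is not among the documents, may specify a retest kit that reports a differential. This cannot be excluded. Section 10.2 prefers central testing but also allows local testing for remote subjects, and does not say what a local laboratory must run.
- **Other safeguards.** Section 8.4 says "Additional clinical laboratory evaluations will be performed at other times if judged clinically appropriate by the PI", or if the safety review suggests it. Symptoms, bilirubin, INR and transaminases are rechecked at each repeat, and an alert from a scheduled visit already has its differential. These narrow the gap, but a mandatory stopping rule should not depend on a discretionary test.
- **Magnitude.** Draw counts are not subjects harmed. The 18–27 figure needs transaminases to rise through a whole 56-day gap without meeting any other rule. This stands: the counts describe the length of the gap, not expected harm.

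**Conclusion.** The concern holds. On off-schedule repeat draws, the plan does not require the one laboratory value needed to apply the eosinophilia limb of a mandatory stopping rule. The limb can go nominally 28 days without a required measurement from Week 4 to Week 48, and 56 days from Week 48 to Week 72.

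The affected group is small: subjects still on drug whose only accompanying sign is new eosinophilia arising between scheduled panels. The 3–17 figure is an upper frame resting on an assumed 1–5% entry rate. No endpoint, threshold or efficacy analysis is affected. The patient-safety value is modest but real, and the correction is cheap enough to be worth making.

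SAP Section 9 records that the sponsor terminated the study in October 2021, and it does not list Section 8.7.2 among the dropped analyses. The practical consequences now are a caveat on that table and corrected text before the protocol is reused.

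**What to change.** In both Section 10.2 lists, replace the red blood count item with the Table 3 hematology panel, stating that it includes the absolute eosinophil count. Align the retest kit and any local laboratory request. No stopping threshold changes.

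A hematology sample is already drawn at each of these visits, so there is no extra visit or needle-stick. The cost is one phrase changed in two places and a small assay charge per repeat draw. For the report of this study, add a footnote to the Section 8.7.2 summary saying that the protocol did not require eosinophils on off-schedule repeats.

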### **8.7.2 Lab Based Stopping Rules**

Summaries will be provided using counts and percentages for subjects who meet the stopping rules as described below:

- If ALT or AST increases to  $>5\times$  Reference baseline (and is at least  $> 5x$  ULN)
- If ALT or AST increases to  $>2\times$  Reference baseline (and is at least  $> 3x$  ULN) AND the increase is accompanied by
  - a concomitant total bilirubin increase to  $>2\times$  Reference baseline (and at least  $> 2x$  ULN) OR
  - the INR is concomitantly  $> 1.5$
- If ALT or AST increases to  $>2\times$  Reference baseline (and is at least  $> 3x$  ULN) AND
  - elevations of ALT/AST are accompanied by signs or symptoms of right upper quadrant abdominal pain, anorexia, nausea, vomiting, fever, eosinophilia ( $>$  upper limit of normal of absolute eosinophilia count), and/or rash.

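### ALT/AST alerts from an elevated baseline that stay below the stopping rules are not counted by treatment group in any analysis the SAP text specifies

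*Protocol*

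**What the plan says.** Protocol 10.2 starts close monitoring when ALT or AST is above 2x Reference Baseline and above 3x ULN, or above 8x ULN. Reference Baseline is the mean of the Screening and Day 1 values (Protocol 10.1; SAP Table 2). The site repeats the tests within 48 to 72 hours, examines the subject, takes a PK sample and asks about alcohol and other exposures. "Should retest results not meet close monitoring cut-offs, a second retest will be requested" and then: "If the second retest is negative, the event will be closed and attributed to the fluctuating nature of liver transaminases".

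The stopping rules in Protocol 10.1 are separate and need no repeat test: "Study drug will be discontinued once any one of the thresholds presented below is met". They are an enzyme-only rule (above 5x Reference Baseline and above 5x ULN) and rules that combine a rise above 2x Reference Baseline and 3x ULN with bilirubin, INR or listed signs and symptoms.

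The SAP specifies these outputs:

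- 8.7.2, on the stopping rules: "Summaries will be provided using counts and percentages for subjects who meet the stopping rules".
- 8.7.2.1, on close monitoring: it restates the alert thresholds and promises a listing. Its opening sentence limits the scope to subjects whose elevation persists on repeat testing and those who stop drug for ALT/AST elevation.
- 8.7.3, on laboratory data: treatment-emergent highs by treatment group, reported above ULN, 2x ULN and 3x ULN. A treatment-emergent high requires a baseline at or below ULN. There are also change-from-baseline summaries and shift tables by visit and treatment group.

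Protocol 3.2 excludes ALT or AST only from 5x ULN upward, and Protocol 3.1 requires AST above 30 IU/L.

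**The concern.** In a NASH population a raised baseline transaminase is within the entry criteria, and the protocol scales its alert to each subject's own Reference Baseline for that reason. The by-arm laboratory count in the SAP is instead anchored to ULN and starts only from a normal baseline. The two definitions part company for subjects who enter above ULN.

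What is at stake is the comparative liver-safety report. A subject who starts at 2x ULN and rises to 6x ULN without symptoms, bilirubin change or INR change triggers the protocol's alert but is not counted by arm in any laboratory summary the SAP describes. If the alert clears on retest, the subject may also be missing from the 8.7.2.1 listing, depending on how its opening sentence is read. AE tables would show the rise only if the investigator recorded it as an AE.

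**Working it through.** The plan states no figure on this point, so there is none to reproduce. The check compares the thresholds, all in multiples of ULN.

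**Step 1: thresholds.** RB is Reference Baseline. From Protocol 10.2, the alert cut-off is min(max(2·RB, 3), 8). From Protocol 10.1, the enzyme-only stop is max(5·RB, 5). The 8.7.3 row counts a value above 3 only if baseline is at or below 1. The table takes Screening and Day 1 as equal.

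| RB | Alert above | Enzyme-only stop above | In the 8.7.3 >3x ULN row? |
|---|---|---|---|
| 1.0 | 3 | 5 | yes |
| 1.2 | 3 | 6 | no |
| 1.5 | 3 | 7.5 | no |
| 2 | 4 | 10 | no |
| 3 | 6 | 15 | no |
| 4 | 8 | 20 | no |
| 4.9 | 8 | 24.5 | no |

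**Step 2: overlap.** The thresholds were compared on a grid in steps of 0.05x ULN, with values up to 10x ULN.

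- Screening and Day 1 both at or below ULN: the 8.7.3 row and the alert pick out exactly the same values (0 mismatches).
- Baseline above ULN and below 5x ULN: of 5,660 grid combinations above the alert and not above the enzyme-only stop, 0 enter the 8.7.3 row.
- Mixed case: the SAP baseline is the last pre-dose value, normally Day 1. With Screening 3 and Day 1 at 1, RB = (3 + 1)/2 = 2 and the alert is above 4. The 8.7.3 row counts this subject from above 3, so it includes every alert plus some values that are not alerts.

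The grid counts threshold combinations, not patients, and says nothing about frequency.

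**Step 3: the other outputs.** SAP 8.7.2 takes only stopping-rule cases. SAP 8.7.2.1 produces a listing and no count. The change-from-baseline summaries include these subjects but only in visit-level aggregates. Protocol 11.7.3 displays shifts as treatment-emergent abnormal, high or low, which cannot isolate a doubling from an already high value.

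**Step 4: does closure after two retests hide large rises?** The documents give no within-subject variability. Assume lognormal variation with CV 10–25%, independent tests, a single enzyme, and RB 1.5–4x ULN, so that the cut-off is 2x RB. For a sustained true level of r times RB, s = √ln(1 + CV²), p = Φ(ln(2/r)/s), and both retests clear with probability p².

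- r = 1.8: 0.730 (CV 10%) to 0.443 (CV 25%)
- r = 2.0: 0.250 at every CV
- r = 2.5: 0.0002 to 0.033
- r = 3.0: at most 0.0025

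At r = 1.8 one test crosses the cut-off with probability 1 − p = 0.145 to 0.334. Over five later visits the chance of at least one new alert is 1 − 0.855⁵ = 0.54 to 1 − 0.666⁵ = 0.87. Large sustained rises therefore rarely clear twice. A level just under the cut-off often clears, but there the crossing itself is variation, and further visits are likely to raise the alert again.

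**The case against.** The strongest reply is that nothing is lost. Every alert value exceeds 3x ULN, and Protocol 8.4 requires all out-of-range results to be judged for clinical significance: "Clinically significant laboratory findings in the opinion of the PI must be recorded as an AE". The board is in place: "Safety data from this study will be reviewed by a Data Safety Monitoring Board (DSMB) throughout the study". SAP 8.7.3 lists all laboratory data with out-of-range flags, and SAP 8.1 puts treatment group on every listing, so a reader could count alerts by hand. The 8.7.2.1 listing can be read broadly because it restates the alert thresholds. SAP 1 places the table shells in a separate document, which may hold such a table. The safety analyses are descriptive, and the study has been terminated.

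Most of this stands, and it sets the size of the point: this is not missing oversight, and no inference depends on it. It does not remove the gap. A listing is not a count, and shells not available here cannot be credited. Even if the 8.7.3 threshold line were read as applying whatever the baseline, a >3x ULN row would mix alerts with subjects who simply entered above 3x ULN. SAP 9 drops many analyses after termination but none in 8.7.

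Two stronger readings are tempting, and the documents support neither.

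- A reader might infer that the closure sentence in Protocol 10.2 fixes the cause in advance and displaces AE recording. The event being closed is most naturally the laboratory alert. Protocol 8.4 and 9.2.2 apply across the study ("The PI must attempt to determine the cause of each event"), and the work-up asks about other causes, including "if the subject started any new medications recently including non-prescription medications and herbal and dietary supplement preparations". Safety laboratory tests recur at every clinic visit. The absent cross-reference is a matter of drafting.
- A reader might infer that alert rates cannot be compared between arms at all. For subjects with normal Screening and Day 1 values, the 8.7.3 row makes that comparison.

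**Conclusion.** The point holds as a minor reporting gap in the SAP. Subjects with baseline ALT or AST above ULN who cross the alert threshold without meeting a stopping rule are not counted by treatment group in any analysis the SAP text specifies. The uncounted band runs from above 3x to 6x ULN at a Reference Baseline of 1.2x ULN, and from above 8x to 20x ULN at 4x, where the bilirubin, INR and symptom criteria are absent.

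This rests on reading the 8.7.3 threshold rows as part of the treatment-emergent definition under which they stand, and on the SAP text without its shells. The documents give neither an alert rate nor the share of subjects above ULN at baseline, so the number affected is unknown. No bias between arms is shown. Protocol 10.2 needs no change on this ground.

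**What to change.** In SAP 8.7.2.1, add counts and percentages by treatment group, with a matching listing, of all safety-population subjects with any post-baseline ALT or AST above 2x Reference Baseline and above 3x ULN, or above 8x ULN. Apply it regardless of baseline status, and flag each subject as cleared or persistent on retest. State that unscheduled results are included, because SAP 8.1 otherwise confines them to listings and the 48–72 hour retests would usually be unscheduled.

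The cost is a short addition to the SAP text, one extra descriptive table and a longer listing. The values are already collected, and Reference Baseline is already a derived variable in SAP Table 2. Nothing changes for sites, and the retest schedule stays as it is.
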